19. At each visit specified in the table, a hepcidin sample will be collected prior to dosing with either study treatment and prior to administration of any iron supplementation.
20. Post-baseline PD samples (i.e., EPO and VEGF) may be taken during any week from Week 28 to Week 52, inclusive, preferably at the earliest opportunity. See Section 9.6 for additional details and requirements for the collection of PD samples.
21. Post-baseline PK samples will be taken at any one of the post-baseline visits indicated in the table, preferably at the earliest opportunity. See Section 9.5 for additional details and requirements for the collection of PK samples.
22. Biomarker samples will be collected and stored for potential future analysis for all participants, except if not permitted by local regulations or IRB/EC, or refused by participant.
23. Participation in genetics research is optional. A separate informed consent signature is required for participation. See Section 9.7 for additional details.
24. Participants who are unable to or require assistance to read must not complete the questionnaires. See Section 9.9 for additional details.
25. Only SAEs, which are assessed as related to study participation or a GlaxoSmithKline (GSK) product, are collected at this visit. See Section 9.2.1 for additional details.
26. Record in the eCRF, if applicable.
27. See details on Rescue in Section 7.9.

Table 2 Schedule of Activities for Participants Who Permanently Discontinue Study Treatment

Procedure	Early Treatment Discontinuation Visit (within 2 weeks of discontinuing study treatment)	Day 1 through Week 52 ¹	
		Week 4, 16, 28, 40, 52 ± 2 weeks	Un-scheduled
IRT system transaction	X	X	X
SBP/DBP, HR (pre- and post-dialysis)	X (triplicate)	X	X
12-lead ECG ²	X		
Iron therapy, transfusions ³	X	X	X
Serum pregnancy test (WOCBP only)	X ⁴		
HemoCue Hgb	X	X	X
Hematology ⁵	X	X	
Clinical chemistry ⁵	X	X	
Ferritin, total iron, UIBC, lipids, iPTH ⁵	X		
Hospitalization, kidney transplant ³	X	X	X
Non-serious AEs, SAEs, AEs of Special Interest, clinical events	X	X	X
Review concomitant medications	X	X	X
PGI-S and PGI-C ⁶	X		

1. Participants will attend those study visits up to Week 52 which have not been completed at the time of early treatment discontinuation. Phone visits are acceptable in exceptional circumstances.
2. ECG assessment may be recorded pre- or post-dialysis.
3. Record in the eCRF, if applicable.

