
 
For the secondary analysis of Hgb change from baseline to Week 52, a mixed model repeated measures (MMRM) approach will be used with an unstructured covariance matrix to compare the difference in means between arms. The model will be fitted to Hgb data collected after baseline up to Week 52, excluding values collected during the stabilization period (Day 1 to Week 28). The model will include factors for treatment, time, prognostic randomization stratification factor (region, see Section 5.3), baseline Hgb and the baseline Hgb by time and treatment by time interaction terms. Analyses will be done with the MIXED procedure in SAS, using the Kenward-Roger option to estimate denominator degrees of freedom and standard errors. This analysis will be performed using all available Hgb values (on and off-treatment) and separately using evaluable Hgb values only (see Section 14.6.3). In the analysis using all available Hgb values, subjects who withdraw from the study before Week 52 are considered to be missing at random and in the analysis using evaluable Hgb values, subjects who permanently discontinue study treatment before Week 52 are assumed to be missing at random.
 
For the analysis of % time in range, the method by Rosendaal [Rosendaal, 1993] will be used to calculate the percentage of time (days) a subject's Hgb is below, within and above the Hgb analysis range of 10 to 11.5 g/dL during the EP (Weeks 28-52). A van Elteren test (stratified Wilcoxon rank sum test) will be used to compare the percentage of time in range between treatment arms, adjusting for treatment and the prognostic randomization stratification factor (see Section 5.3). This analysis will be performed using evaluable Hgb
 

values only. Hodges-Lehmann estimate of the treatment difference will be used to assess non-inferiority in % time in range.
 
 
For the Hgb responder analysis, mean Hgb during the EP will be defined as in the while on-treatment evaluable Hgb supportive analysis (Section 14.6.3). Responders will be subjects with a mean Hgb during the EP that falls within the Hgb analysis range of 10-11.5 g/dL. A Cochran-Mantel-Haenszel (CMH) chi-squared test, adjusting for treatment and the prognostic randomization stratification factor (region as randomized, see Section 5.3), will be used to compare the number and % of responders between the treatment groups.
 

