#### 14.4.1.1. Study Phases for Hgb, Iron Parameters, IV Iron Dose Endpoints, Iron Use Summaries, Transfusion and PRO Data

Study Phase	Definition
Pre-Treatment	Date $\leq$ Study Treatment Start Date
On-Treatment	Study Treatment Start Date < Date $\leq$ Study Treatment Stop Date + 1 day
Post-Treatment	Date > Study Treatment Stop Date + 1 day
Post-Randomization	Randomization Date < Date

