### 14.6.3. Efficacy

#### 14.6.3.1. Hemoglobin Endpoints

Hemoglobin Values
Central Laboratory and HemoCue Hgb Values

 
When source of Hgb measurement is not specified: 
 
For reporting purposes, central laboratory Hgb values will be used, unless otherwise specified. However, if a central laboratory Hgb value is missing, a corresponding non-missing HemoCue Hgb value will be used. This approach will be used for the primary Hgb analysis.
 
 
 
Some displays may be created for either central laboratory Hgb values only or HemoCue Hgb values only. The central laboratory summary will be considered the primary summary in this case.
 

Evaluable Hemoglobin Values

 
Evaluable Hgb values are on-treatment Hgb values (see Section 14.4.1) that are not taken within the 8 weeks following a red blood cell transfusion, a whole blood transfusion, or a non-randomized ESA treatment which occurs on or after the randomization date.
 
Red blood cell transfusions, whole blood transfusions and non-randomized ESA treatments occurring on or after the randomization date are identified by comparing the start and stop date of the respective transfusion or ESA concomitant medication record to the randomization date.
 

Imputed Hemoglobin Values

 
For each missing value between baseline to Week 52 (inclusive), 200 imputed values will be generated using the multiple imputation method (see Section 7.1.5). The average of these 200 imputed values will be used as the value for this missing value in the summary tables and figures.
 

CONFIDENTIAL

204837

Hemoglobin Values					

 
For primary efficacy Hgb analysis and the corresponding subgroup analyses using all available observed and imputed Hgb values (on and off-treatment), Rubin's rules [Rubin, 1987] will be used to combine results of the imputed datasets using SAS PROC MIANALYZE procedure.
 
					
EP Hemoglobin Value for Primary Hgb Analysis					

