
 
The scenarios outlined below provide guidance on the use of unscheduled Hgb values and multiple Hgb values occurring on the same date. Each row represents a single calendar date.
 
Rows outlining scenarios where there is at least one central lab Hgb and at least one HemoCue Hgb on the same date apply only for the derivation of Hgb values to be used in the primary Hgb analysis, where central lab values are used if they are available and if the central lab value is missing, then a corresponding non-missing HemoCue Hgb value is used.
 
Rows outlining scenarios involving combinations of scheduled and unscheduled Hgb values of the same type apply to all Hgb summaries and analysis.
 
					
Scheduled Central Lab Hgb Value	Unscheduled Central Lab Hgb Value	Scheduled HemoCue Hgb Value	Unscheduled HemoCue Hgb Value	Value to Use	Type/Label
x				Scheduled central lab Hgb value	Scheduled visit
	x			Unscheduled central lab Hgb value	Unscheduled
		x		Scheduled HemoCue Hgb value	Scheduled visit
		multiple 		Average of scheduled HemoCue Hgb values	Scheduled visit
			x	Unscheduled HemoCue Hgb value	Unscheduled
	multiple			Average of unscheduled central lab Hgb values	Unscheduled

CONFIDENTIAL

204837

Hemoglobin Values					
			multiple	Average of unscheduled HemoCue Hgb values	Unscheduled
x	x			Average of central lab Hgb values	Scheduled visit
x		x		Scheduled central lab Hgb value	Scheduled visit
x			x	Scheduled central lab Hgb value	Scheduled visit
	x	x		Unscheduled central lab Hgb value	Unscheduled
	x		x	Unscheduled central lab Hgb value	Unscheduled
		x	x	Average of HemoCue Hgb values	Scheduled visit

1: The dose adjustment algorithm will require sites to obtain two HemoCue Hgb values at some visits.

Time In Range
Time in Range During the EP

 
Number of days that a subject's evaluable Hgb is within the analysis range of 10-11.5 g/dL inclusive during the EP (See Section 14.6.1), including any unscheduled evaluable Hgb values that were taken during this time period.
 
Use of unscheduled Hgb values follows the scenarios for unscheduled and multiple Hgb values.
 
Linear interpolation is used to estimate Hgb between visits, accounting for any intermittent missing values (Rosendaal, 1993).
 

Percent Time in Range During the EP

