
 
Time in Range During the EP / [Earlier of (Treatment Stop Date+1, Week 52 visit date) – Week 28 visit date]
 
Note: Percent time in/below/above range during the EP is only defined for subjects with a Treatment Stop Date that is after their Week 28 visit date, and have at least two evaluable Hgb values on different days, where at least one evaluable Hgb value is contained within the EP and another evaluable Hgb value occurs within the range of the Week 16 visit through 4 weeks following the Week 52 visit, inclusive.
 

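### Percent time in range divides by on-treatment days after the last evaluable hemoglobin, which no rule in the SAP classifies, so those days count as not in range

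*SAP*

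**What the plan says.** SAP 7.3.1 plans to calculate the percentage of days on which a participant's "Hgb is below, within and above the Hgb analysis range of 10 to 11.5 g/dL during the EP", citing a published method. SAP 14.6.3.1 gives the one stated rule for assigning days: "Linear interpolation is used to estimate Hgb between visits, accounting for any intermittent missing values". The percentage is then time in range divided by "Earlier of (Treatment Stop Date+1, Week 52 visit date) – Week 28 visit date".

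The eligibility note beneath it reads "Percent time in/below/above range during the EP is only defined for subjects with a Treatment Stop Date" later than the Week 28 visit. It also asks for two evaluable values on different days: one inside the evaluation period (EP), and a second where "another evaluable Hgb value occurs within the range of the Week 16 visit through 4 weeks following the Week 52 visit". The two values need not reach both ends of the denominator.

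Three further definitions decide which values count and how long the denominator runs:

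- Evaluable values are on-treatment values "that are not taken within the 8 weeks following a red blood cell transfusion, a whole blood transfusion, or a non-randomized ESA treatment" (SAP 14.6.3.1).
- A hemoglobin value is post-treatment when "Date > Study Treatment Stop Date + 1 day" (SAP 14.4.1.1). Protocol Table 2 describes the visit after stopping as "Early Treatment Discontinuation Visit (within 2 weeks of discontinuing study treatment", so its hemoglobin will often fall outside the on-treatment window.
- If the Week 52 visit is missing, SAP 14.6.1 substitutes the planned date, so the denominator still runs to Week 52.

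**The concern.** The numerator can only contain days that lie between two evaluable values. The denominator contains every day from Week 28 to the end of treatment or Week 52. When the last evaluable value falls before that end, the remaining days are divided by but belong to no category. In effect, an unmeasured day is scored as a day out of range.

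A participant never seen out of range can then score well below 100%. If below and above use the same denominator, the three percentages do not add up, and time below range is understated. Two programmers could also reasonably fill the gap differently. If one arm had more early stopping or late transfusion, the comparison would move against that arm for a reason unrelated to measured hemoglobin.

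**Working it through.** The documents give no worked value or sample size for this endpoint, so there is no figure to reproduce. The check applies the SAP rule to planned visit days.

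**Inputs.** Count days from Week 28 (day 0). Visits fall every 28 days to Week 52 (day 168), from the protocol schedule. A value is evaluable if its day is no later than stop + 1 (SAP 14.4.1.1) and not within 56 days after a transfusion or non-randomized ESA (SAP 14.6.3.1). Assume every evaluable value is in range and the Week 28 value is present.

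**Formula.** Score = last evaluable day ÷ min(stop day + 1, 168).

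| Case | Last evaluable day | Denominator | Score |
|---|---|---|---|
| Complete to Week 52 | 168 | 168 | 100% |
| Stop two days before Week 36 (day 54) | 28 (Week 32) | 54 + 1 = 55 | 28/55 = 51% |
| Stop two weeks after Week 44 (day 126) | 112 (Week 44) | 126 + 1 = 127 | 112/127 = 88% |
| Transfused at Week 45, treatment continued; Weeks 48 and 52 excluded | 112 (Week 44) | 168 | 112/168 = 67% |
| Week 52 missed, no later evaluable value | 140 (Week 48) | 168 | 140/168 = 83% |
| Only EP value at Week 28, another at Weeks 16 to 24, stop at Week 31 (day 21) | 0 | 21 + 1 = 22 | 0/22 = 0%, or 1/22 = 5% if the Week 28 day is counted |

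**All stop days from 1 to 166.** For 26 of them no visit after Week 28 is evaluable. The other 140 have a mean score of 83.9% (minimum 50.9%). With the 26 counted as zero, the overall mean is 140 × 83.9 ÷ 166 = 70.8%.

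**Sum of the three categories.** If below and above share the denominator, below + within + above equals the same ratio: for example 83% when Week 52 is missed.

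**Between arms.** The documents give no arm-specific rates, so these are assumptions: 268 versus 134 participants, the same hemoglobin distribution in both arms under three assumed settings, stop dates uniform over the EP and unrelated to hemoglobin, 150 replicates, Monte Carlo SE at most 0.1. The entry is the Hodges-Lehmann difference (daprodustat − rhEPO) under the SAP denominator minus the same difference with interpolated days as denominator.

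| Assumed rates, daprodustat vs rhEPO | Shift in points, three settings |
|---|---|
| Stopping 10% vs 10% | −0.12, 0.00, +0.05 |
| Stopping 20% vs 10% | −1.71, −0.93, −1.50 |
| Stopping 30% vs 10% | −3.44, −2.07, −3.13 |
| Stopping 10% vs 20% | +1.76, +0.88, +1.34 |
| Transfusion or ESA in Weeks 44 to 52, 10% vs 3% | −1.22, −0.46, −0.94 |

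If stopping instead follows a fall in hemoglobin (assumed 1.5 g/dL over eight weeks), carrying the last value forward gives a lower difference than interpolated days: by 0.3 to 0.6 points at 20% vs 10% and by 1.0 to 1.3 points at 30% vs 10%.

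**The case against.** **The cited method may already cover this.** SAP 7.3.1 and 14.6.3.1 adopt a published method that was not available here. It may say what to do outside the first-to-last measurement. That limits the claim to what the SAP text says. If a rule exists, the SAP should state it, because its own denominator is explicit and its own description stops at interpolation between visits.

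**The shared denominator is inferred.** The formula is written only for time in range. That below and above share it is read from the eligibility note, which names all three, and from the programming note to Table 2.032, which has each participant contribute to each category. This stands as an inference.

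**An eligible participant scores exactly 0%.** A reader might infer this for someone whose only EP value is Week 28. The documents do not settle it: SAP 14.6.1 defines the EP as inclusive, which would give 1/22. Near 0% is as far as the text goes.

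**Start gaps.** A reader might treat the start of the EP as an equal problem. The Week 16 limit is an eligibility condition, and nothing limits how far back interpolation reaches. Even with such a limit, Weeks 16, 20, 24 and 28 span 84 days while one exclusion lasts 56, so one transfusion or one ESA dose cannot remove all four values. Start gaps are possible but rare.

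**Completers.** A reader might also infer that completers lose their last interval, because a last dose two days before Week 52 gives 140/167 = 84%. The documents do not say whether a dose is given that day, and the per-protocol criteria count seven scheduled EP values. This is conjecture.

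**Interpolated days are not the truth either.** This stands. The simulated shift compares two rules. With hemoglobin-related stopping, interpolated days favor the arm that stops more, relative to carry-forward. Without a minimum span, values only at Weeks 28 and 32 would move from 28/168 = 17% to 100%. A minimum is therefore a required part of the change.

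**Conclusion.** The point holds for end gaps. As written, SAP 14.6.3.1 scores unmeasured on-treatment days at the end of the period as not in range. The size for an affected participant is clear: 51%, 67% or 83% in the main examples, where every measured value is in range. This rests on planned visit days and on applying no extrapolation rule.

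A reader might infer that the treatment comparison is biased. The documents do not support that. They give no arm-specific rates of stopping or late transfusion. The shift is about zero with balanced arms and the same hemoglobin distribution, and about 1 to 3 points under the assumed stopping imbalances. All of this lies well inside the 15-point reference margin. Secondary analyses are exploratory (Protocol 10.3.1) and not adjusted for multiplicity (SAP 5.5). This is a low-priority clarification, worth making because it is cheap while the data are blinded.

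**What to change.** Before unblinding, amend SAP 14.6.3.1 as follows:

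- Use as denominator the EP days spanned by interpolation between evaluable values, counted as elapsed days in both numerator and denominator. This also settles the mismatch between an inclusive EP (169 days) and a denominator of 168.
- Treat a participant with less than a stated minimum span as undefined; 28 days, one visit interval, is an example.
- Apply the same rule to below, above and the percentage of time at 12 g/dL or higher (SAP 7.4.1), and check that below + within + above = 100%.
- Keep two sensitivity analyses: the current denominator, and the last evaluable value carried forward to the earlier of stop + 1 and Week 52. They are needed because stopping can depend on hemoglobin; Protocol Table 8 ties rescue discontinuation to persistently low values.

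The cost is a short SAP amendment, one new denominator for four percentages, one check and two extra runs. A few participants become undefined: with uniform stop dates and a 28-day minimum, 26/166 = 15.7% of those who stop in the EP, or about 1.6% of an arm at 10% stopping and 3.1% at 20%. Short spans are noisier, and days after a late transfusion leave the main measure. Protocol 3 says the trial is matched as far as possible to the once-daily study. Whether that study uses the current denominator is not stated; if it does, the first sensitivity analysis keeps the results comparable.

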### 14.6.3.2. Iron Endpoints

Iron Endpoints
Iron Medications

 
During the study, subjects may be receiving iron in multiple routes, including: 
 
IV iron
 
Oral iron
 
Other iron (including intramuscular, subcutaneous, and hemodialysis/dialysate)
 
 
 
Note: The iron route categories above will be determined using the route on the Prior/Concomitant Medication – Iron Therapy record. In addition, ferric citrate records recorded on the Prior/Concomitant Medication – Metabolic Bone Disease Therapy eCRF form will also be summarized as oral iron use.
 

**Iron Endpoints****Baseline Iron Use**

- The number and percentage of subjects in the following iron use categories at baseline will be summarized:
  - IV iron use only
  - Oral iron use only
  - Other iron use only
  - IV and oral iron use only
  - IV and other iron use only
  - Oral and other iron use only
  - IV, oral, and other iron use
  - No iron use
- When determining baseline iron use, the gap factors mentioned below in the IV iron standardization algorithm will be applied to the end date for each iron record, and the baseline period of 12 weeks before the Randomization date until the day before the Randomization date will also be used.

**Standardized IV Iron Dose (mg/week) to Determine Iron Management Action**

- In order to compare between IV iron records, to determine the action taken with IV iron therapy in the 8 weeks following the date the IV management threshold was met, the dose of IV iron in each associated record will be standardized in terms of mg/month.
- IV iron therapy concomitant medication records that occur or are ongoing during the 8 weeks following the date the IV management threshold was met (inclusive), will be selected and ordered by start and end date.
  - If there is a record has a start date on the date the IV management threshold was met, and a prior record has an end date on the day before the IV management threshold was met, this prior record will be selected and considered as well.
- The standardization will be carried out with the following formula:
  - Standardized IV iron dose (mg/week) = IV iron drug dose (mg) \* frequency

Note: Frequency defined as follows:

Frequency (from eCRF)	Frequency (for standardization formula)
2 times per week	2
3 times per week	3
4 times per week	4
5 times per week	5
BID	14
Once daily	7
One time dose	1
Every 12 Hours	14
Every 2 weeks	0.5
Every 4 weeks	0.25
Once a month	0.23
Once a week	1

CONFIDENTIAL

204837

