- Average quarterly TSAT while on treatment will be summarized by presenting average TSAT values for the quarters used to generate IV iron dose by quarter (see Section 14.6.3). Summaries will include mean, standard deviation, minimum, P25, median, P75, and maximum by treatment group. Graphical summaries will be provided.
- Average quarterly ferritin while on treatment will be summarized by presenting average ferritin values by quarter (see Section 14.6.3). Summaries will include geometric mean, coefficient of variation, minimum, P25, median, P75, and maximum by treatment group. Graphical summaries will be provided.
- The number and percentage of subjects that met the iron management criteria during the study while on treatment will be summarized by treatment group for each 3-month period of the study and across the entire study. There are two types of iron management thresholds: the first type requires that iron therapy be administered if subjects have ferritin and/or TSAT values that are too low; the second type requires that all iron (excluding multivitamins) must be stopped if ferritin and/or TSAT values are too high. It is also possible for a subject to meet starting and stopping criteria on the same day with a low ferritin and a high TSAT. These subjects will also be summarized (see Section 14.6.3). Assessment of meeting iron management thresholds will be made based on central laboratory data values. at the scheduled visits for ferritin and TSAT assessments, according to the schedule outlined in the Schedule of Activities table (see Section 14.2.1). Further, the subjects who met the threshold requiring iron administration to start or stop while on IV iron will be grouped by the action taken with IV iron therapy in the 8 weeks following the date the threshold was met (i.e., starting or increasing iron therapy, maintaining existing iron therapy, receiving no iron therapy, stopping or decreasing iron therapy with no increase, Section 14.6.3) according to concomitant medication records for IV iron.
- The number and percentage of subjects that reduced IV iron supplementation relative to baseline during the EP while on treatment will be summarized by treatment group (see Section 14.6.3).

- A stacked bar chart of on-treatment iron use will be created by treatment group to show the percentages of subjects with different types of iron use at baseline and at each quarter post-baseline.

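### The iron-management action grouping scores a one-time IV iron dose as if it were given weekly, so some reductions in iron can be reported as increases

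*SAP*

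**What the plan says.** SAP 7.4.1 (Iron Parameters) takes subjects who crossed a start or stop threshold while on IV iron. It says that they "will be grouped by the action taken with IV iron therapy in the 8 weeks following the date the threshold was met", the groups being "starting or increasing iron therapy, maintaining existing iron therapy, receiving no iron therapy, stopping or decreasing iron therapy with no increase". Section 14.6.3 is cited for the details.

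The derivation is in SAP 14.6.3.2, under the heading on the standardized IV iron dose used to determine the iron management action. It selects IV iron records that occur or are ongoing in the 8 weeks after the threshold date. A record that ended the day before that date is added only if another record starts on the date itself. It announces that "the dose of IV iron in each associated record will be standardized in terms of mg/month", but the formula begins "Standardized IV iron dose (mg/week) = IV iron drug dose (mg" and multiplies by a frequency factor. The factor table includes "One time dose 1", "Every 2 weeks 0.5", "Every 4 weeks 0.25" and "Once a month 0.23"; once a week is also 1. No duration, gap factor or total-dose step follows.

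The derivations of baseline IV iron dose, dose to Week 52 and dose in the evaluation period, later in 14.6.3.2, use the same factor of 1 for a one-time dose. They pair it with a duration of 7 days and then compute the record total as standardized dose times duration divided by 7.

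**The concern.** A factor of 1 per week is a rate. For a one-time dose it gives the right amount only if the rate is held for one week, which is what the 7-day duration does in the dose endpoints. The action derivation takes over the factor without the duration, so one infusion carries the same score as that infusion repeated every week.

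A reduction to a single infusion can then look like an increase. The grouping amplifies this, because a subject is placed in the stopping-or-decreasing group only if no increase was found, so one false increase removes the subject from it. After a low-iron threshold the table could credit an increase that did not occur. After a high-iron threshold it could show a reduction as an increase. What is at stake is how Table 2.057 describes the response to the iron management criteria in Protocol 7.8.1.

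**Working it through.** **Inputs from the documents.** The frequency factors, the formula and the 8-week window come from the action derivation in SAP 14.6.3.2. The 7-day duration comes from the dose-endpoint derivations in the same section. SAP 14.6.1 sets 1 month = 30.4375 days.

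**Assumptions.** The documents give no typical IV iron dose, so the doses below are illustrative. The earlier schedule is taken to stop at the threshold date and to be among the selected records. An increase is taken to mean a higher standardized dose in the later record.

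**Step 1: reproduce the SAP's factors.** A recurring factor should equal 7 divided by the days between doses.
- Every 2 weeks: 7/14 = 0.5.
- Every 4 weeks: 7/28 = 0.25.
- Once a month: 7/30.4375 = 0.23.

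The recurring factors agree with the table.

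**Step 2: the one-time factor.**
- With the 7-day duration: D × 1 × 7/7 = D mg, which is the amount given.
- As a rate over the 8-week window: 1/8 = 0.125 doses per week.
- Ratio of scored to average rate: 1/0.125 = 8.

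**Step 3: when the direction reverses.** Let the earlier schedule average W mg/week and let the single dose be D mg. The comparison scores W against D. The iron given over 8 weeks is 8W against D.
- D < W: scored as a decrease, and it is one.
- D = W: scored as maintained, although iron falls by 1 − 1/8 = 87.5%.
- W < D < 8W: scored as an increase, although iron falls.
- D > 8W: scored as an increase, and it is one.

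For D = 100 mg the reversed range is W from 100/8 = 12.5 up to 100 mg/week. Multiplied by 30.4375/7, that is about 54 to 435 mg/month.

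**Step 4: examples.**

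| Earlier schedule | Single dose | Scored (mg/week) | Class | 8-week total (mg) | True change |
|---|---|---|---|---|---|
| 100 mg every 2 weeks | 100 mg | 50 → 100 | increase | 400 → 100 | −75% |
| 100 mg every 4 weeks | 100 mg | 25 → 100 | increase | 200 → 100 | −50% |
| 100 mg once a month | 100 mg | 23 → 100 | increase | 184 → 100 | −46% |
| 100 mg weekly | 100 mg | 100 → 100 | maintained | 800 → 100 | −87.5% |
| 100 mg 3 times a week | 100 mg | 300 → 100 | decrease | 2400 → 100 | −96% |
| 100 mg weekly | 500 mg | 100 → 500 | increase | 800 → 500 | −37.5% |
| 100 mg 3 times a week | 500 mg | 300 → 500 | increase | 2400 → 500 | −79% |
| 100 mg weekly | 1000 mg | 100 → 1000 | increase | 800 → 1000 | +25% |

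At equal dose per infusion, the reversal occurs for schedules less frequent than weekly. A cut from weekly is scored as maintained. A cut from two or more infusions a week is still correctly a decrease. A larger single dose carries the reversal to more frequent schedules.

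**Step 5: the unit label.** Converting mg/week to mg/month multiplies every score by 30.4375/7 = 4.35. The order of the records is unchanged, so the mismatch in wording alters no classification.

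**The case against.** The strongest reply is that the SAP never states how ordered records become an increase, a maintenance or a decrease, so the misclassification depends on a reconstructed rule. That is fair, and the result above is conditional for this reason. But the derivation exists to compare IV iron records, a higher score is the natural reading of an increase, and leaving the rule unwritten is a second gap.

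Record selection narrows the case further. If the earlier schedule ran on into the window, its infusions count too and the true fall is smaller. If it ended well before the threshold date, it is normally not selected and the single dose would read as a start. The examples need the switch to happen at about the threshold date.

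It can also be said that Protocol 7.8.1 sets start and stop rules, not rules to raise or lower iron. One infusion after a low threshold is iron given, and any infusion during a stop period departs from the rule whichever group it falls in. This stands: the grouping is not a clean measure of adherence. It does not make a rank of 8 times the average rate correct.

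A reader might go further and infer any of the following, which the documents do not support:
- **Every cut to a single infusion is reported as an increase.** Step 3 shows the condition.
- **Starting or increasing is overstated overall.** Nothing indicates how often one-time records replace schedules or in which direction the errors net out, and the same algorithm applies to both arms.
- **Several one-time doses rank the same as one, so a real increase is shown as maintained.** This depends on the unwritten rule, and an earlier one-time dose is normally outside the selected records.
- **The principal secondary IV iron result is distorted, or rests on Table 2.057.** Its one-time records carry the 7-day duration, and neither document gives the table that supporting role.

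**Conclusion.** The concern holds in a limited form. The action derivation applies a stated factor that ranks a one-time dose at 8 times its average rate over the 8-week window, and it omits the duration step that makes the same factor correct in the dose endpoints. This is an error in the rule, not merely missing detail.

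Given the assumptions listed in the working, a reduction to a single dose D can be reported as an increase when D lies between W and 8W, and as maintained when D equals W.

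The reach is small: the action grouping in Table 2.057, which is exploratory and descriptive with no test planned. The counts of subjects meeting the thresholds use central laboratory ferritin and TSAT and are unaffected, as is the principal secondary endpoint. This is a minor point, worth correcting because it is cheap.

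**What to change.** In SAP 14.6.3.2, class the action by comparing total IV iron (mg) in the 8 weeks after the threshold date with the total in the 8 weeks before it. Compute both totals as in the dose-endpoint derivations, with a 7-day duration for one-time records so that each counts once. Write out the rule for increase, maintain and decrease, including what to do when the later window is cut short. Correct the mg/month label to match the formula, or drop it if totals are used.

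Changing the one-time factor to 0.125 and summing overlapping records would not be enough. One-time doses on different dates do not overlap, so they would still not be added together.

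The cost is SAP wording and a small amount of extra programming. No new data are needed: the derivation of dose to Week 52 already selects IV iron records from 12 weeks before randomization, and the longest look-back, from a threshold met on Day 1, reaches 8 weeks before it.
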